***C. Difficile* Stool Testing**

During the Screening Period a stool sample will be collected and sent to the central laboratory for testing. The sample will be assessed for the presence of *C. difficile* toxin.

The sample must be shipped to the central laboratory using dry ice. Additional information is available in the Investigator Manual provided by the central laboratory.

Subjects who are positive for *C. difficile* toxin may be treated appropriately and re-screened.

Pharmacokinetics

Blood samples for adalimumab and anti-adalimumab (AAA) will be collected starting at Baseline (Week 0). Time points are indicated in [Table 1](#).

Blood samples for Infliximab and Human Anti-Chimeric Antibody (HACA) will be collected at Baseline (Week 0).

5.3.1.2 Blood Samples for Pharmacogenetic Analysis

One 4 mL whole blood sample for DNA isolation will be collected at the time points indicated in [Table 1](#) from each subject who consents to provide samples for pharmacogenetic analysis. The procedure for obtaining and documenting informed consent is discussed in [Section 9.3](#).

Instructions for the preparation and shipment of pharmacogenetic samples will be provided in the lab manual. Samples will be shipped frozen to the central laboratory in China and then to an AbbVie designated laboratory in China for long-term storage. Samples should not be allowed to thaw prior to arrival at the designated laboratory. Arrangements will be made with the central laboratory for the shipment of PG samples to the specified lab for testing in China.

Samples will be stored in a secure storage space with adequate measures to protect confidentiality. The samples will be retained while research on adalimumab (or drugs of this class) continues but no longer than 10 years.

5.3.1.3 Blood Samples for Biomarkers Analysis

Collection of Samples for mRNA Assays

One 2.5 mL blood samples for mRNA will be collected at the time points indicated in [Table 1](#) from each subject who consents to provide samples for mRNA analysis. The procedure for obtaining and documenting informed consent is discussed in [Section 9.3](#).

Instructions for the preparation and shipment of biomarker samples will be provided in the lab manual. Samples will be shipped frozen to the central laboratory in China and then to an AbbVie designated laboratory in China for long-term storage. Samples should not be allowed to thaw prior to arrival at the designated laboratory. Arrangements will be made with the central laboratory for the shipment of mRNA samples to the specified lab for testing in China.

Samples will be stored in a secure storage space with adequate measures to protect confidentiality. The samples will be retained while research on adalimumab (or drugs of this class) continues but no longer than 10 years.

5.3.2 Drug Concentration Measurements

5.3.2.1 Collection of Samples for Analysis

Blood samples for adalimumab, AAA, infliximab, and HACA assays will be obtained at the time points as indicated in [Table 1](#).

The time that each blood sample is collected will be recorded to the nearest minute in the source document and on the appropriate eCRF.

Collection of Samples for Adalimumab and AAA Assays

Blood samples for adalimumab and AAA assays will be collected by venipuncture into appropriately labeled 4 mL evacuated serum collection tubes (one tube for adalimumab and one tube for AAA) without gel separator immediately prior to dosing. Sufficient blood will be collected to provide approximately 2 mL serum for adalimumab assay and 2 mL serum for AAA assay. Blood will be allowed to clot for 30 – 60 minutes at room temperature before centrifugation.

A maximum of 9 samples are planned to be collected per subject for adalimumab (5 samples) and AAA (4 samples) assays if the subject does not dose escalate. If the subject dose escalates, a maximum of 11 samples are planned to be collected per subject for adalimumab (6 samples) and AAA (5 samples) assays. If all subjects dose escalate, the total number of samples planned will not exceed 1200 (6 samples × 200 subjects) for the adalimumab assay and 1000 (5 samples × 200 subjects) for the AAA assay for the entire study.

Collection of Samples for Infliximab and HACA Assays

Blood samples for infliximab and HACA assay will be collected at Week 0 (Baseline) by venipuncture into appropriately labeled 4 mL evacuated serum collection tube without gel separator at Baseline (Week 0). The sample will be obtained immediately prior to dosing. Blood will be allowed to clot for 30 – 60 minutes at room temperature before

centrifugation. Sufficient blood will be collected to provide approximately two 1 mL serum specimens (one tube for infliximab and one tube for HACA).

The total number of samples planned will not exceed 400 (2 samples × 200 subjects) for the entire study.

5.3.2.2 Handling/Processing of Samples

The blood samples for adalimumab, AAA, infliximab, and HACA assay will be labeled with information such as the following: the type of sample, the study drug number, protocol number, subject number, study week/visit name, and assay type (pharmacokinetic [PK]-Adalimumab or AAA; PK-Infliximab or HACA).

Additional detailed instructions for the handling and processing of samples will be provided from the central laboratory.

Handling/Processing of Adalimumab and AAA Assays

The blood samples for adalimumab and AAA assay will be centrifuged at 1100 – 1600 × g for 10 – 15 minutes within 30 – 60 minutes of collection to separate the serum. The serum samples will be transferred using plastic pipettes into screw-capped polypropylene vials labeled with information such as the following: the study drug name, protocol number, subject number, study week/visit name, and assay type (Pharmacokinetics [PK] Adalimumab or AAA). The serum samples will be frozen within 2 hours after collection and will remain frozen in a –20°C or colder freezer until shipped. Sites that do not have access to a –20°C or colder freezer will need to ship the samples the day they are collected.

Samples will be shipped frozen from the sites to the designated laboratory in China for testing and storage. Samples should not be allowed to thaw prior to arrival at the designated laboratory.

Additional detailed instructions for the handling and processing of samples will be provided from the central laboratory/AbbVie.

Handling/Processing of Infliximab and HACA Assays

The blood samples for Infliximab and HACA assay will be centrifuged at 1100 – 1600 × g for 10 – 15 minutes within 30 – 60 minutes of collection to separate the serum. The serum samples will be transferred using plastic pipettes into screw-capped polypropylene vials labeled with information such as the following: the study drug number, protocol number, subject number, study week/visit name, and assay type (Infliximab or HACA). The serum samples will be frozen within 2 hours after collection and will remain frozen in a –20°C or colder freezer until shipped. Sites that do not have access to a –20°C or colder freezer will need to ship the samples the day they are collected.

Samples will be shipped frozen to the designated laboratory in China for testing and storage. Samples should not be allowed to thaw prior to arrival at the designated laboratory.

Additional detailed instructions for the handling and processing of samples will be provided from the central laboratory/AbbVie.

5.3.2.3 Disposition of Samples

Frozen serum samples will be packed in dry ice (pellet form) sufficient to last 3 days during transport. Samples will be shipped pursuant to instructions from the onsite CRA. An inventory of the samples will be included in the package for shipment. Arrangements will be made with the central lab for the transfer of samples.

5.3.2.4 Measurement Methods

Serum concentrations of adalimumab and AAA will be determined using a validated ligand binding assay (LBA) method under the supervision of the Bioanalysis Department at AbbVie.

5.3.3 Efficacy Variables

5.3.3.1 Primary Variable

The primary efficacy variable is the proportion of subjects who achieve clinical remission (CDAI < 150) at Week 4.

5.3.3.2 Secondary Variables

The Week 26 efficacy endpoint is proportion of subjects who achieve clinical remission at Week 26 (CDAI < 150) in subjects who achieved clinical response (decrease in CDAI \geq 70 points from Baseline) at Week 8.

Key secondary efficacy endpoints include:

- Proportion of subjects who achieve CDAI < 150 plus a reduction in hs-CRP of at least 50% from Baseline at Week 4.
- Proportion of subjects who achieve CDAI < 150 plus a reduction in hs-CRP of at least 50% from Baseline at Week 26 in subjects who achieved decrease in CDAI \geq 70 points from Baseline plus at least 30% reduction in hs-CRP from Baseline at Week 8.
- Proportion of subjects who discontinue corticosteroid use and achieve clinical remission (CDAI < 150) at Week 26 in subjects who were taking steroids at Baseline and who achieved clinical response (decrease in CDAI \geq 70 points from Baseline) at Week 8.
- Proportion of subjects who discontinue corticosteroid use and achieve CDAI < 150 plus a reduction in hs-CRP of at least 50% from Baseline at Week 26 in subjects who were taking steroids at Baseline and who achieved decrease in CDAI \geq 70 points from Baseline plus a reduction in hs-CRP of at least 30% from Baseline at Week 8.
- Proportion of subjects who achieve clinical response (decrease in CDAI \geq 70 points from Baseline) at Week 4.
- Proportion of subjects who achieve decrease in CDAI \geq 70 points from Baseline plus a reduction in hs-CRP of at least 30% from Baseline at Week 4.

- Proportion of subjects who achieve CDAI < 150 and hs-CRP < 3 mg/L at Week 4.
- Proportion of subjects who achieve CDAI < 150, hs-CRP < 3 mg/L at Week 26 in subjects who achieved clinical response (decrease in CDAI \geq 70 points from Baseline) at Week 8.
- Proportion of subjects who achieve IBDQ remission (IBDQ \geq 170 points) at Week 4.
- Proportion of subjects who achieve IBDQ remission at Week 26 in subjects with clinical response (decrease in CDAI \geq 70 points from Baseline) at Week 8.
- Change from Baseline in fecal calprotectin level at Week 4.
- Proportion of subjects who achieve CDAI < 150, hs-CRP < 3 mg/L and fecal calprotectin < 250 μ g/g at Week 4.
- Proportion of subjects who achieve CDAI < 150, hs-CRP < 3 mg/L and fecal calprotectin < 250 μ g/g at Week 26 in subjects who achieved clinical response (decrease in CDAI \geq 70 points from Baseline) at Week 8.

Additional secondary endpoints include:

- Proportion of subjects with clinical remission (CDAI < 150) over time.
- Proportion of subjects with CDAI < 150 plus a reduction in hs-CRP of at least 50% from Baseline over time.
- Proportion of subjects with clinical response (decrease in CDAI \geq 70 points from Baseline) over time.
- Proportion of subjects with decrease in CDAI \geq 70 points from Baseline plus a reduction in hs-CRP of at least 30% from Baseline over time.
- Change from Baseline in CDAI over time.
- Change from Baseline in hs-CRP level over time.
- Change from Baseline in fecal calprotectin level over time.

5.3.4 Safety Variables

Safety analyses will be performed on all subjects who receive at least one dose of study drug. Incidence of adverse events, changes in vital signs, physical examination results, and clinical laboratory data will be assessed.

5.3.5 Pharmacokinetic Variables

Serum adalimumab concentrations will be determined from samples collected just prior to dosing at Baseline (Week 0), Week 4, Week 8, Week 12, and Week 26/Premature Discontinuation. Blood samples for the measurement of serum adalimumab concentrations at Week 14, Week 16, Week 18, Week 20, Week 22 and Week 24 will be collected prior to dosing only if the subject qualifies for dose escalation.

Serum anti-adalimumab antibody (AAA) will be determined from the samples collected just prior to dosing at Baseline (Week 0), Week 4, Week 12 and Week 26/Premature Discontinuation. Blood samples for the measurement of serum AAA at Week 14, Week 16, Week 18, Week 20, Week 22 and Week 24 will be collected prior to dosing only if the subject qualifies for dose escalation.

Blood samples will also be collected for measurement of infliximab serum levels and HACA just prior to dosing at Baseline (Week 0).

5.3.6 Pharmacogenetic Variables

DNA samples may be sequenced and data analyzed for genetic factors contributing to the disease or the subject's response to adalimumab, or other study treatment, in terms of pharmacokinetics, efficacy, tolerability and safety. Such genetic factors may include genes for drug metabolizing enzymes, drug transport proteins, genes within the target pathway, or other genes believed to be related to the disease (examples include but are not limited to LCN2, CCL20, NOD2) or drug response. Some genes currently insufficiently characterized or unknown may be understood to be important at the time of analysis. The samples may be analyzed as part of a multi-study assessment of genetic factors involved in the response to adalimumab, drugs of this class, or the disease. The samples may also

be used for the development of diagnostic tests related to adalimumab, drugs of this class, or disease. The results of pharmacogenetic analyses may not be reported with the study summary.

5.3.7 mRNA Variables

Samples from subjects may be analyzed for mRNA expression levels contributing to the subject's response to disease or study treatment, in terms of pharmacokinetics, pharmacodynamics, efficacy, tolerability and safety. Messenger RNA levels related to disease or response to drug therapy will be measured in peripheral whole blood. For analysis, mRNA expression may be analyzed using a microarray and polymerase chain reaction (PCR) technique in peripheral blood samples. This analysis will measure the levels of essentially all mRNAs present in the collected peripheral blood samples. Messenger RNA analysis will be limited to studying response to Crohn's disease; no other analyses will be performed. Results of biomarker mRNA are considered exploratory and may not be included in the study summary.

5.4 Removal of Subjects from Therapy or Assessment

5.4.1 Discontinuation of Individual Subjects

A subject may withdraw from the study at any time. The Investigator may discontinue any subject's participation for any reason, including an adverse event, safety concerns or failure to comply with the protocol.

Subjects will be withdrawn from the study immediately if any one of the following occurs:

- Clinically significant abnormal laboratory result(s) or adverse event(s), as determined by the Investigator in consultation with the AbbVie SDP.
- The Investigator believes it is in the best interest of the subject.
- The subject requests withdrawal from the study.

- Inclusion and exclusion criteria violation was noted after the subject started study drug, when continuation of the study would place the subject at risk as determined by the AbbVie SDP (see Section 5.2 and Section 7.0).
- Introduction of prohibited medications or dosages when continuation of the study drug would place the subject at risk as determined by the AbbVie SDP.
- Subject is non-compliant with TB prophylaxis.
- Subjects with negative TB Screening before Week 0 who later develop a positive/indeterminate QuantiFERON-TB Gold In-Tube test result or CXR/chest CT findings.
- The subject becomes pregnant while on study drug.
- Subject has dysplasia or a malignancy, except for localized non-melanoma skin cancer. Discontinuation for carcinoma in-situ of the cervix is at the discretion of the Investigator.
- Subject is diagnosed with lupus-like syndrome, multiple sclerosis or demyelinating disease.
- Subject is significantly non-compliant with study procedures which would put the subject at risk for continued participation in the trial, as determined by the Investigator, in consultation with the AbbVie SDP.

If, during the course of study drug administration, the subject prematurely discontinues study drug use, the procedures outlined for the Premature Discontinuation Visit must be completed within 2 weeks of the last dose of study drug, and preferably prior to the initiation of another therapy. However, these procedures should not interfere with the initiation of any new treatments or therapeutic modalities that the Investigator feels are necessary to treat the subject's condition. Following discontinuation of the study drug, the subject will be treated in accordance with the Investigator's best clinical judgment.

A final phone call will be made to the subject approximately 70 days after the last dose of study drug to determine the status of any ongoing AEs/SAEs or the occurrence of any new AEs/SAEs. The information will be recorded on the appropriate eCRF page. The 70-day follow-up phone call will not be required for any subject who initiates adalimumab therapy not supplied in the context of the clinical trial after the end of study participation.

All attempts must be made to determine the date of the last dose of study drug and the primary reason for premature discontinuation. The information will be recorded on the appropriate eCRF page.

For subjects who are considered lost to follow-up, reasonable attempts must be made to obtain information on the final status of the subject. At a minimum, two phone calls must be made and one certified letter must be sent.

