- h. Subjects with negative QuantiFERON-TB Gold In-Tube test within 35 days of Screening will not require a repeat test, if documentation is available. Subjects with a negative QuantiFERON-TB Gold In-Tube test during the Screening Period will have repeated QuantiFERON-TB Gold In-Tube test at Weeks 2, 4, 6, 8, 12, 16, 20, and 26/PD, unless the Investigator has decided to initiate TB prophylaxis in that subject. For subjects with an indeterminate result during the Screening period, a repeat Screening period test should be performed unless the Investigator decides to initiate TB prophylaxis. If the repeat testing result during the Screening period is negative the QuantiFERON-TB Gold In-Tube test result is considered negative, but if the repeat testing result is indeterminate or positive TB prophylaxis should be initiated at least 3 weeks before Baseline. Subjects who have a negative QuantiFERON-TB Gold In-Tube test result during Screening and later develop a positive result will be withdrawn from the study. Subjects who have a negative QuantiFERON-TB Gold In-Tube test result during Screening and later develop an indeterminate result will have repeat testing and will be withdrawn from the study if the repeat testing confirms indeterminate or positive results.
- i. Chest x-ray includes posterior-anterior (PA) and lateral views. Subjects with a normal (or one with non-clinically significant findings) CXR within 35 days of Screening would not require a repeat CXR, if documentation is available. All subjects will have repeated CXRs performed to evaluate for TB during the study at Weeks 8, 16, and 26/Premature Discontinuation. A chest CT scan may be used instead of the CXR at investigator discretion. If CXR or chest CT scan was obtained within 4 weeks of Premature Discontinuation, a repeat CXR/chest CT scan is not required.

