In the assessment of CXR/chest CT scan, a **radiologist** must note the presence or absence of 1) calcified granulomas, 2) pleural scarring/thickening, and 3) signs of active TB as well as the presence of hilar and/or mediastinal lymphadenopathy. In the assessment of the CXR or chest CT scans at Weeks 8, 16, and 26/PD, a radiologist must compare the results to the Screening image and note the presence of the above factors as well as the presence of hilar and/or mediastinal lymphadenopathy. The Principal Investigator (or designee) will indicate the clinical significance of any findings and will sign and date the report.

TB Screening

All subjects should be screened for latent TB infection (LTBI), including those with a prior history of BCG administration.

LTBI screening consists of:

- QuantiFERON-TB Gold In-Tube test (QTF),
- CXR (or chest CT, at the Investigator's [or designee] discretion),
- Medical history of contact with active TB.

During Screening Period:

If any one of the three assessments (QTF, CXR/CT or medical history) is positive, the subject will be considered to have LTBI and will receive TB prophylaxis.

For subjects with an indeterminate QTF result during the Screening period, a repeat Screening period test should be performed with another blood or the subject must initiate TB prophylaxis prior to enrolling in the study. If the repeat testing result during the Screening period is negative the QTF test result is considered negative, but if the repeat testing result is indeterminate or positive TB prophylaxis should be initiated.

In the assessment of the Screening period CXR/chest CT scan, a radiologist must note the presence or absence of 1) calcified granulomas, 2) pleural scarring/thickening, and 3) signs of active TB as well as the presence of hilar and/or mediastinal lymphadenopathy. The Principal Investigator must indicate the clinical significance of any findings and contact the AbbVie SDP to discuss any clinically significant abnormal findings before enrolling the subject. The Principal Investigator (or designee) will sign and date each report.

Subjects who have a diagnosis of LTBI during Screening and do not initiate prophylaxis cannot be enrolled.

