Subjects who have a diagnosis of LTBI and agree to initiate prophylaxis should be consulted with a TB specialist (a physician with TB treatment knowledge and experience) regarding the selection of the appropriate TB prophylaxis regimen as per Centers for Disease Control (CDC) recommendations or local guidelines.

Initiation of TB prophylaxis in subjects with negative LTBI screening is permitted during the Screening period as warranted based on the opinion of the investigator.

Subjects with an LBTI diagnosis or those in whom TB prophylaxis is electively initiated will receive TB prophylaxis for at least 21 days (before or on the Day -21 visit) prior to Baseline (Week 0), and are required to have a Day -21 and Day -7 visits. At Day -21,

the CDAI and hs-CRP must be obtained and must meet the entry criteria in Section 5.2. For the calculation of the CDAI on Day –21, the hematocrit value obtained at the first screening visit will be used. After initiation of TB prophylaxis, subjects will return to the clinical site 7 days (at Day –7) prior to Baseline (Week 0) to have safety labs drawn, including hs-CRP. The hematocrit and hs-CRP values obtained at Day –7 will be used to calculate the Baseline (Week 0) CDAI to confirm eligibility for study enrollment.

All subjects who initiate TB prophylaxis should continue the prophylaxis regimen for the duration of the subject's participation in the study, including the 70-day follow-up period. TB prophylaxis may only be initiated during the Screening period and is not permitted to be initiated during the study. If the Investigator feels initiation of TB prophylaxis is warranted after the subject has been randomized, the subject must be withdrawn from the study.

Prophylactic treatment for TB should be captured on the concomitant medications page in the eCRF and in the source documents. Prior therapy should be captured in medical history.

After Week 0:

All subjects will be monitored for signs and symptoms suggestive of active TB at all visits.

Subjects who initiate TB prophylaxis should continue the prophylaxis regimen for the duration of the subject's participation in the study and the study follow-up period. These subjects will not require repeat QTF testing but will undergo repeat chest imaging at Weeks 8, 16, and 26/Premature Discontinuation.

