Subjects who are negative for LTBI during screening and are not taking TB prophylaxis will have their QTF repeated at Weeks 2, 4, 6, 8, 12, 16, 20, and 26/Premature Discontinuation and the chest imaging repeated at Weeks 8, 16, and 26/Premature Discontinuation.

In the assessment of the CXR or chest CT scans at Weeks 8, 16, and 26/PD, a radiologist must compare the results to the Screening image and note the presence of the following factors 1) calcified granulomas, 2) pleural scarring/thickening, and 3) signs of active TB, as well as the presence of hilar and/or mediastinal lymphadenopathy. The Principal Investigator must indicate the clinical significance of any findings and contact the AbbVie SDP to discuss any clinically significant abnormal findings and determine the next steps. The Principal Investigator (or designee) will sign and date each report.

Subjects who have a negative QTF test result during Screening and later develop a positive QuantiFERON-TB Gold In-Tube test result will be withdrawn from the study.

Subjects who have a negative QTF test result during Screening and later develop an indeterminate result will have repeat testing and will be withdrawn from the study if the repeat testing result is indeterminate or positive.

TB prophylaxis is not permitted to be initiated during the study.

For subjects who develop signs and symptoms suggestive of active TB or with negative TB Screening who are withdrawn later from the study due to a positive/indeterminate QuantiFERON-TB Gold In-Tube test result or CXR/chest CT findings, a TB specialist (a physician with TB treatment knowledge and experience) should be consulted regarding appropriate patient management.

Table 2. Chart for TB Assessments at Screening and After Week 0

Screening Period				After Week 0	
QTF	CXR/CT	Medical History	TB Prophylaxis Required	Monitoring For:	
				LTBI	Active TB
+	+	+	Yes	No	Yes [^]
+	+	-	Yes	No	Yes [^]
+	-	+	Yes	No	Yes [^]
+	-	-	Yes	No	Yes [^]
-	+	+	Yes	No	Yes [^]
-	-	+	Yes	No	Yes [^]
-	+	-	Yes	No	Yes [^]
-	-	-	No	Yes*	Yes [^]

* During follow-up, subjects who are negative for LTBI during screening and are not taking TB prophylaxis will have their QTF repeated at Weeks 2, 4, 6, 8, 12, 16, 20, and 26/Premature Discontinuation and the chest imaging repeated at Weeks 8, 16, and 26/Premature Discontinuation. Subjects who are negative for LBTI during Screening who initiate TB prophylaxis per the Investigator's discretion do not require repeat QTF testing.

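### Protocol 5.4.1 withdraws subjects at once for an indeterminate QuantiFERON result, with no repeat step; 5.3.1.1 and Table 1 note h withdraw only if the repeat is indeterminate or positive

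*Protocol*

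**What the plan says.** The list in Protocol 5.4.1 opens with "Subjects will be withdrawn from the study immediately if any one of the following occurs". For TB it names "Subjects with negative TB Screening before Week 0 who later develop a positive/indeterminate QuantiFERON-TB Gold In-Tube test result", together with chest imaging findings. A positive and an indeterminate result are treated alike. The bullet has no repeat step and no section reference, although another bullet in the same list does carry one (to Sections 5.2 and 7.0).

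Protocol 5.3.1.1 (TB Screening, After Week 0) separates the two results. A positive result after a negative screening test leads to withdrawal. Subjects with an indeterminate result "will have repeat testing and will be withdrawn from the study if the repeat testing result is indeterminate or positive". Table 1 note h of the Protocol agrees: such a subject "will be withdrawn from the study if the repeat testing confirms indeterminate or positive results". Table 1 note h of the SAP carries the same text.

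Screen-negative subjects not on TB prophylaxis are tested at Weeks 2, 4, 6, 8, 12, 16, 20 and 26 or at premature discontinuation. Section 7.0 makes it a reportable deviation to keep a subject who has met a withdrawal criterion.

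**The concern.** A site cannot both withdraw a subject at once on a first indeterminate result and hold that subject for a retest. Nothing in the Protocol says which section governs. The two rules lead to different actions in exactly one case, an indeterminate result followed by a negative repeat.

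A site that acts on 5.4.1 alone would take a subject off treatment for a result that a retest could clear. If that subject is a Week 8 responder, the Week 26 CDAI would normally be missing, and non-responder imputation (NRI) would count the subject as not in remission. The Week 26 endpoint is a single-group comparison with a fixed 30%, so each such loss lowers the observed remission rate.

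**Working it through.** **The texts side by side**

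| Finding after a negative screen | 5.4.1, read literally | 5.3.1.1 and Table 1 note h |
|---|---|---|
| Positive | Withdraw | Withdraw |
| Indeterminate, repeat positive or indeterminate | Withdraw (at the first result) | Withdraw (after the repeat) |
| Indeterminate, repeat negative | Withdraw | Keep |

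Only the last row differs in outcome. No conflict is claimed for positive results or for chest imaging.

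**Would the Week 26 CDAI be missing?** The last scheduled test before Week 26 is at Week 20 (nominal Day 141, SAP Table 2). Suppose the result arrives late enough that a Week 22 dose is still given, at the end of its window: Day 155 + 3 = Day 158. The discontinuation visit "must be completed within 2 weeks of the last dose of study drug", so by Day 158 + 14 = Day 172. The Week 26 CDAI window is Days 177 to 190. The value would normally be missing, and SAP 6.0 scores it as not achieved.

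**The plan's own figure.** Protocol 8.2 states at least 99% power for 52% against 30% with 100 responders, by a one-sample exact test. Under 30%, P(X ≥ 39) = 0.0340 and P(X ≥ 40) = 0.0210, so the test rejects at 40 or more. P(X ≥ 40 | 0.52) = 0.9939. The stated figure reproduces.

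**Illustration of size.** The documents give no indeterminate rate, so the following are assumptions:
- r = indeterminate rate per test, constant, with results independent within a subject
- four tests at risk (Weeks 8, 12, 16, 20)
- 20% of indeterminate results confirmed on repeat
- 100 responders, all retested
- s = 0.5, the share of subjects at sites that read 5.4.1 literally

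Formulas:
- Literal rule: wL = 1 − (1 − r)^4
- Repeat rule: wR = 1 − (1 − 0.2r)^4
- Mixture: w = s·wL + (1 − s)·wR
- Extra withdrawals per 100 = 100·s·(wL − wR)
- Remission rate = 0.52·(1 − withdrawn fraction), then power = P(X ≥ 40)

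| r | wL | wR | Extra per 100 | Power, repeat rule | Power, mixture | Loss (points) |
|---|---|---|---|---|---|---|
| 0.5% | 0.0199 | 0.0040 | 0.8 | 99.3% | 99.1% | 0.2 |
| 1% | 0.0394 | 0.0080 | 1.6 | 99.2% | 98.8% | 0.4 |
| 3% | 0.1147 | 0.0238 | 4.5 | 98.8% | 96.3% | 2.5 |
| 5% | 0.1855 | 0.0394 | 7.3 | 98.2% | 91.0% | about 7 |

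For example, at 5%: w = 0.5 × 0.1855 + 0.5 × 0.0394 = 0.1124. The remission rate is 0.52 × 0.8876 = 0.4615.

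The comparator is the repeat rule, not the 99.4% design figure, because confirmed indeterminate results cause withdrawals under the intended rule as well.

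**Sensitivity**
- At 5% per test, shares of 10% and 25% instead of 50% give 97.4% and 95.7%, losses of 0.8 and 2.5 points from 98.2%.
- Section 8.2 ties its figure of 100 responders to a Week 8 response rate above 50%. With 140 responders (assumed), the test rejects at 54 or more (upper tail 0.0185), and the 5% and 50% case gives 97.1%.
- Retesting all responders is an upper bound, because subjects on TB prophylaxis have no repeat QuantiFERON.

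**The case against.** The strongest reply is that the 5.4.1 bullet is shorthand. Section 5.3.1.1, shortly after setting out the repeat rule, refers to subjects "who are withdrawn later from the study due to a positive/indeterminate QuantiFERON-TB Gold In-Tube test result or CXR/chest CT findings". That is nearly the wording of the 5.4.1 bullet, used for results that have already passed through the repeat rule. At screening the same logic holds: "If the repeat testing result during the Screening period is negative the QTF test result is considered negative". Three places state the repeat rule and one summary list omits it. This is persuasive about intent, and it is why the point is minor. It does not remove the mismatch. In 5.3.1.1 the phrase describes subjects already withdrawn, whereas in 5.4.1 it is itself the trigger and stands alone under an instruction to act immediately.

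A reader might infer that a site which repeats the test commits a reportable deviation under Section 7.0. The documents do not support that. The site would be following the specific procedure in 5.3.1.1 and Table 1, and it would deviate only if the literal 5.4.1 text overrode both. The wording leaves room for a query, not for a finding of non-compliance.

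It is also fair to object that the power figures rest entirely on assumed rates. They do. The mismatch in the text needs none of them.

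**Conclusion.** The inconsistency is real, is in the current text, and is minor. An operative withdrawal criterion, read as written, gives the wrong action for a subject whose indeterminate result is cleared on repeat.

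The size cannot be established from the documents. Under the stated assumptions, with half of subjects at literal-reading sites, the loss of Week 26 power is about 0.4 points at 1% indeterminate per test and about 7 points at 5%. It is material only if the rate is several percent and many sites also read 5.4.1 literally.

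Two stronger readings should be resisted:
- **That the Week 26 conclusion is at risk of being too favourable.** The error runs the other way. Extra failures lower the rate compared with 30%. The planned LOCF analysis (SAP 10.3) and observed-case analysis (SAP 6.0) would help show how much the extra missing values matter.
- **That the Week 4 primary endpoint or the sample size is affected.** The documents give no rate from which such an effect could be shown, and the 5.4.1 wording applies alike to both arms. No effect on either is claimed.

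**What to change.** Reword the 5.4.1 bullet so that it covers subjects with negative TB screening before Week 0 who later have (a) a positive QuantiFERON result, (b) an indeterminate QuantiFERON result that is indeterminate or positive on repeat testing (see Section 5.3.1.1), or (c) CXR/chest CT findings.

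Attach the cross-reference to clause (b) only. Placed after the imaging clause, it would bring in the 5.3.1.1 step in which the investigator and the study-designated physician settle what to do next about significant imaging findings. That would alter a trigger on which no conflict is claimed. Withdrawal for a positive result and for imaging findings stays as it is. So does the separate rule in 5.3.1.1: "If the Investigator feels initiation of TB prophylaxis is warranted after the subject has been randomized, the subject must be withdrawn from the study".

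The cost is one bullet at the next protocol amendment and a clarification letter to sites until then. No new data item or analysis is needed, and the SAP already carries the repeat rule.
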